Determination of Abnormal Fetal Growth or Amniotic Fluid with Third Trimester Ultrasounds in Uncomplicated Pregnancies: A Randomized Trial (UP Trial)

NCT02702999

Version Date: 05/03/2016

Determination of Abnormal Fetal Growth or Amniotic Fluid with Third Trimester Ultrasounds in Uncomplicated Pregnancies: A Randomized Trial (UP Trial)

Protocol

INVESTIGATORS Principal

Investigator: [name], MD

Co-investigators:

[name]

[name], MS

[name]

[name] [name], MD

Department of Obstetrics, Gynecology, and Reproductive Sciences, Division of Maternal-Fetal Medicine, University of Texas at Houston Health Science Center

PICO Question:

P: Women with uncomplicated pregnancies in the third trimester (30 weeks or more)

I: Ultrasound to assess fetal growth and amniotic fluid every 4 weeks, starting at 30 weeks.

C: Uncomplicated pregnancies who have clinically indicated obstetric ultrasound

O: Ultrasound diagnosis of abnormal growth or of abnormal amniotic fluid after 30 weeks.

1 Background

1.1 Abnormal Fetal Growth or Amniotic Fluid in 3rd Trimester

Abnormal fetal growth is defined as an estimate of less than 10% (fetal growth restriction; FGR) or greater than 90% (excessive growth) for gestational age. Amniotic fluid is considered to be low (oligohydramnios) if the single deepest vertical pocket is less than 2 cm or if amniotic fluid index is less than 5.0 cm, and it is regarded as being excessive (polyhydramnios) if the single deepest vertical pocket is greater than 8 cm or if the amniotic fluid index is \geq 24 cm. The reason for accurately identifying these 4 conditions is that they are linked with adverse pregnancy outcomes, also known as peripartum complications. FGR, for example, is associated with stillbirth, cesarean for non-reassuring fetal heart rate tracing, neonatal seizure, sepsis, and neonatal death. Excessive fetal growth, also known as large for gestational age (LGA), or macrosomia, is associated with prolonged labor, cesarean delivery, traumatic birth, neurologic injury and death. Oligohydramnios is associated with stillbirth, emergency cesarean delivery, low Apgar score, and fetal anomalies. Lastly, polyhydramnios is associated with abruption, stillbirth, and postpartum hemorrhage (Table 1).

To minimize the complications with these four conditions, clinicians in the 3rd trimester have to identify these pregnancies, start antepartum surveillance, and time the delivery based on gestational age and the results of surveillance (Table 1).

	Abnormalities of fetal growth		Abnormalities of amniotic fluid	
	FGR	LGA	Oligohydramnios	Polyhydramnios
Definition	Birth weight <	Birth weight	SDP < 2.0 cm or	SDP > 8 cm or
	10% for GA	> the 90%	AFI < 5.0 cm	AFI >  24.0 cm
		for GA		
Rate in US	10%	10%	3%	7%
Increased risk of				

Table 1. Abnormalities of fetal growth or of amniotic fluid

	Abnormalities of fetal growth		Abnormalities of amniotic fluid	
	FGR	LGA	Oligohydramnios	Polyhydramnios
Stillbirths	Yes		Yes	Yes
CD—NR FHRT	Yes		Yes	Yes
Traumatic birth		Yes		
Neonatal seizure	Yes			
Intubation	Yes			
Neonatal death	Yes	Yes	Yes	Yes
Intervention to improve				
outcomes				
NST / AF assessment	Yes		Yes	Yes
Umbilical Doppler	Yes			
Serial US for growth	Yes	Yes	Yes	Yes
Induction at 37-39 wks	Yes	Yes	Yes	Yes
or earlier				
Scheduled cesarean	Yes	Yes		
Considered identified if	EFW < 10%	EFW > 90%	SDP <2.0 cm or	SDP > 8.0 cm or
			AFI < 5.0 cm	AFI> 24.0 cm
Identified in published	10-50% (11-17)	10% (18)	1% (20)	3% (20)
reports				

FGR, fetal growth restriction; LGA, large for gestational age; SDP, single deepest pocket; AFI, amniotic fluid index (summation of four SDP); CD-NR FHR, cesarean delivery for non-reassuring fetal heart rate tracing; EFW, estimated fetal weight

1.2 Current Methods of Detecting Abnormal Fetal Growth or Amniotic Fluid

The current guidelines by American College of Obstetricians and Gynecologists (ACOG) indicate that women without complications or co-morbidities should have their fundal height measured at prenatal visits. If the difference between fundal height and gestational age is 3 or more then ultrasound exam (USE) consisting of fetal growth and assessment of amniotic fluid should be undertaken (7).

When performing USE based on indications the detection of abnormal growth is poor because majority are undetected. A summary of 7 publications from 6 countries indicates that only 1 out of 3 FGR infants were identified before birth (Table 2). Similarly, Heywood et al reported that at a teaching hospital, only 11% of newborns with excessive growth were identified before delivery. Alternatively if ultrasound exam is done within 4 weeks of delivery, then over 60% of abnormal growth is identified (19). A recent multi-center pilot randomized trial among uncomplicated pregnancies noted that with USE in the 3rd trimester, 67% of FGR were identified during pregnancy compared to 9% with routine care; 80% of LGA were identified with USE compared to 0% with routine care (20). Thus, a randomized trial is warranted to assess if serial

USE after 30 weeks, when compared to current routine care, increases the identification of abnormal conditions before birth.

	Published in	Country	Births	FGR Detected
Jahn A et al (12)	1998	Germany	2,339	32%
Lindqvist PG et al	2005	Sweden	24,585	54%
(13)				
McCowan LM et al	2010	Aus, NZ, UK	5,606	27%
(14)				
Mattioli KP et al (15)	2010	USA	1,502	10%
Verlijsdonk JW et al	2012	Netherlands	4,247	37%
(16)				
Chauhan SP et al	2013	USA	11,487	25%
(17)				
Monier I et al (18)	2015	France	14,100	22%
Total			63,926	31%

Table 2. Antepartum detection of small for gestational age

Aus, Australia; NZ, New Zeeland, UK, United Kingdom, USA, United States of America

2 Study Design

2.1 Primary Research Question

The primary research question is: In women at a gestational age of 30 weeks or more without comorbidities, does performance of serial 3rd trimester growth ultrasounds increase the frequency of identifying abnormalities in estimate of fetal growth (< 10% or > 90% for gestational age) or amniotic fluid (oligohydramnios or polyhydramnios), when compared with women who only receive indicated ultrasounds?

2.2 Secondary Research Questions

- Among women with abnormal growth identified on ultrasound, what is the rate of newborns with a birth weight < 10% or > 90% for gestational age?
- What is the composite neonatal morbidity among (CNM; defined below) among women with serial versus indicated USE? CNM is any of the following: 1) Apgar score < 5 at 5

min, 2) umbilical arterial pH < 7.00, 3) intraventricular hemorrhage grade III or IV, 4) periventricular leukomalacia, 5) intubation for over 24 hrs, 6) necrotizing enterocolitis grade 2 or 3, 7) stillbirth or 8) death within 28 days of birth.

(Intraventricular hemorrhage was classified by Papile's criteriawith grade III hemorrhage being associated with ventricular dilatation and grade IV with parenchymal extension. Necrotizing enterocolitis was diagnosed in the presence of more than one clinical sign, such as bilious gastric aspirate or emesis, abdominal distention, occult or gross fecal blood, and at least one radiographic finding of pneumatosis intestinalis, hepatobiliary gas, or pneumoperitoneum.) (24)

• What is the composite maternal morbidity (CMM) among those with serial vs indicated USE? CMM is defined as any of the following: 1) chorioamnionitis, 2) cesarean delivery in labor, 3) wound infection, 4) transfusion, 5) deep venous thrombus or pulmonary embolism, 6) admission to intensive care unit or 7) death.

(Chorioamnionitis defined as clinical findings of maternal fever, and maternal and fetal tachycardia in the absence of other localizing signs of infection. Wound infection defined as tenderness, erythema, or discharge associated with cesarean skin incision.) (26 & 27)

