The third trimester ultrasounds will follow the American Institute of Ultrasound in Medicine (2007) guidelines. In particular, biparietal diameter (BPD) will be measured at the level of thalami and insula, and measurement taken from outer edge of the proximal skull to the inner edge of the distal skull. The head circumference (HC) will be measured at the same level as the biparietal diameter, around the outer perimeter of the calvaria. Since HC is not affected by head shape, it will be used if the head is flattened (dolichocephaly) or rounded (brachycephaly). Abdominal circumference (AC) measurement will be determined at the skin line on a true transverse view at the level of the junction of the umbilical vein, portal sinus and the fetal stomach. Femoral length (FL) will be measured with the beam of insonation being perpendicular to the shaft, excluding the distal femoral epiphysis (Chervenak 1998, ACOG 2009). Estimated fetal weight will be derived using the regression equation proposed by Hadlock (1985): Log_{10} (EFW) = $1.5662 - 0.0108(HC) + 0.0034(HC)^2 + 0.0468(AC)+0.171(FL)-0.003685(AC)(FL) with EFW being estimated fetal weight; HC, head circumference; AC, abdominal circumference, and; FL, femur length. If a fetal anomaly which was not noted in early survey is discovered during the <math>3^{rd}$ trimester USE, clinicians and women be informed.

Abnormalities of fetal growth are fetal growth restriction (FGR) and large for gestational age (LGA). A fetus will be considered to have FGR if the estimated fetal weight is < 10% for gestational age and LGA if the estimate is > 90% for gestational age. Amniotic fluid will be estimated using single sonographic deepest pocket (SDP), which involves finding and vertically measuring the largest cord-free pocket of amniotic fluid or will be calculated by the sum of the maximum vertical pockets in all 4 quadrants. Oligohydramnios, or decreased amniotic volume, is a SDP less than 2 cm or amniotic fluid index < 5.0 cm; hydramnios, or excessive amniotic fluid, is a SDP >8 cm or amniotic fluid > 24.0 cm(ACOG 2009).

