3.3 Patient Management

Clinicians managing these women will be informed of the sonographic findings if any of the following is noted: 1) FGR or estimated fetal weight < 10% for gestational age, 2) LGA or estimated fetal weight > 90% for gestational age, 3) oligohydramnios, 4) hydramnios, or 5) sonographic findings which influences clinical management e.g. spontaneous bradycardia or previously undetected fetal anomaly. Women with abnormal findings will be notified. They will also be informed that their clinicians are aware and management will be according to guidelines and departmental practices (Table 3).

Abnormalities seen on Ultrasound	Recommendation to Clinicians
FGR (estimated fetal weight < 10% for GA)—from ACOG Practice Bulletin # 134 (reference 7)	 Unless previously done, perform a detailed fetal anatomic survey Serial ultrasound evaluations of the following: (1) Fetal growth with Doppler velocimetry (every 3- 4 weeks) (2) Biophysical profile with or without non-stress test (weekly) along with umbilical artery Dopplers One course of antenatal corticosteroids between 24 and 34 weeks of gestation in the week before delivery is expected Delivery at 38-39 weeks or sooner if abnormal results of antepartum testing or co-
LGA (estimated fetal weight)— from ACOG Practice Bulletin # 22 (reference 22)	 If EFW is ≥ 5,000 in non-diabetic, recommend primary cesarean delivery
 Oligohydramnios—from ACOG Practice Bulletin # 145 (reference 2) 	 Consider a repeat fetal structural survey to rule out possible missed a fetal malformation Non-stress test (NST) and AFI (or biophysical profile) once or twice weekly until delivery For women with idiopathic oligohydramnios, we suggest delivery at 36 to 37 completed weeks of gestation rather than expectant management
Polyhdyramnios—(reference 23)	 A repeat comprehensive sonographic evaluation is recommended to determine whether fetal anomalies or fetal hydrops is present. Suggested laboratory evaluations depend upon

Table 3. Abnormal findings and recommendation to clinicians

Abnormalities seen on	Recommendation to Clinicians	
Ultrasound		

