3.4 Study Outcome Measures and Ascertainments

3.4.1 Primary outcome:

The primary outcome is presence of SGA (EFW<10%), LGA (EFW>10%), oligohydramnios, or polyhydramnios among uncomplicated pregnancies that have indicated versus serial USE starting at 30 weeks or more. These parameters are not based on any outcomes after birth.

3.4.2 Secondary outcomes:

- Composite Neonatal Morbidity (CNM) among the two groups
- Composite Maternal Morbidity (CMM) among the two groups.

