3.4.3 Statistical Analysis

Intention to treat analyses will be performed. The rate of the primary outcome, abnormal fetal condition (estimated fetal weight < 10% or > 90% for GA, oligohydramnios or polyhydramnios), will be compared between the intervention and control group using a log binomial (or Poisson in case of nonconvergence) model with treatment group as a covariate to estimate relative risk and 95% confidence interval (CI). The definition of the primary outcome is presence of FGR (EFW<10%), LGA (EFW>90%), oligohydramnios, or polyhydramnios and is not based on any outcomes after birth. Therefore there is no issue about false-positives or false-negatives.

Each secondary outcome will be analyzed similarly. Based on the MFMU Network data that stated CNM occurs in 1.9% of women with uncomplicated pregnancies, we estimate that over 29,000 women need to be randomized to show one-third improvement in CNM (power 90%) among uncomplicated women that have routine ultrasound exams vs. those that have indicated ultrasound examinations. Hence our purpose for these outcomes is to calculate unbiased estimates to provide information for the large multicenter trial in MFMU Network.

We will also conduct a Bayesian analysis of the primary outcome to calculate probability of treatment benefit or harm. We will use a neutral prior distribution for the intervention effect that excludes implausible large treatment effects: Normal (0, SD=0.70) in the log RR scale (prior 95% interval for the RR of 0.23-4.35) (28) Point estimates of treatment effect and 95% credible intervals will be reported with posterior probabilities of benefit and/or harm.

4 Ethics

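### Secondary question 1 asks for one pooled birth-weight rate across FGR and LGA calls, so it cannot show how often either diagnosis was right (minor, cheap to fix)

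*Combined protocol and SAP*

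**What the plan says.** Section 2.2 opens its secondary questions with "Among women with abnormal growth identified on ultrasound, what is the rate of newborns with a birth weight < 10% or > 90" (both cut-offs are percentiles). The denominator is every woman with any abnormal growth finding on ultrasound. The numerator is a newborn in either tail of birth weight.

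Elsewhere the plan keeps the two growth diagnoses apart:

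- Section 3.1 defines them separately: "A fetus will be considered to have FGR if the estimated fetal weight is < 10% for gestational age and LGA if the estimate is" above the 90th percentile.
- Table 3 (section 3.3) gives them separate entries. The FGR entry covers surveillance and delivery timing. The LGA entry is a single line: "If EFW is ≥ 5,000 in non-diabetic, recommend primary cesarean delivery".

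The outcome and analysis sections do not take the question further. Section 3.4.2 lists only "Composite Neonatal Morbidity (CNM) among the two groups" and the corresponding maternal composite. Section 3.4.3 says that secondary outcomes are analysed like the primary, and describes no predictive value, direction-specific rate or cross-table. On the primary outcome, which is defined without reference to the newborn, it says: "Therefore there is no issue about false-positives or false-negatives".

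**The concern.** The primary outcome counts ultrasound findings, whether or not the newborn bears them out. Secondary question 1 is therefore the only place where the plan compares a growth call with birth weight. Readers will naturally want it to say how often a call of FGR, or of LGA, was correct.

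As worded it cannot do that, for two reasons:

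1. **Merging.** A single rate over FGR and LGA calls is an average of two predictive values, weighted by how many calls of each kind were made. If the two values differ, the average describes neither.
2. **No matching of direction.** Read literally, a fetus called FGR and born above the 90th percentile enters the numerator, as does the reverse.

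Section 3.4.3 says that the secondary estimates are meant to inform a large multicenter trial. Planning such a trial would need the accuracy of FGR and LGA calls separately.

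**Working it through.** The documents give no figure for this question, so there is none to reproduce. The checks below measure how far the pooled rate can mislead.

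**Inputs from the documents**

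- Rates of birth weight <10% and >90%: 10% each (Table 1, section 1.1).
- Share of affected newborns identified with third-trimester ultrasound in the pilot trial: FGR 67%, LGA 80% (section 1.2).
- Expected primary-outcome rates: 25% intervention, 10% control, with 103 women per group (section 2.4).

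**Inputs assumed**

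- Predictive values of 30% (FGR) and 60% (LGA), for illustration.
- Bivariate normal z-scores for estimated fetal weight and birth weight, with 10% tails.

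**Step 1: merging**

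Correctly identified cases per 100 women are 10 × 0.67 = 6.7 (FGR) and 10 × 0.80 = 8.0 (LGA). These are true positives, not calls. Calls are true positives divided by predictive value:

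- FGR calls: 6.7 / 0.30 = 22.3
- LGA calls: 8.0 / 0.60 = 13.3
- Pooled rate: (6.7 + 8.0) / (22.3 + 13.3) = 14.7 / 35.7 = 41%

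That is 41 − 30 = 11 points above the FGR value and 60 − 41 = 19 points below the LGA value.

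These inputs imply growth calls in about 36% of women. Section 2.4 expects 25% with any growth or fluid finding, so the example shows the mechanism and is not a forecast. The mechanism does not depend on the number of calls. With FGR share w of all calls, the pooled rate is 0.30w + 0.60(1 − w): 52.5% at w = 0.25, 45% at w = 0.50 and 37.5% at w = 0.75. The same two predictive values give different pooled rates as the mix of calls changes.

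**Step 2: direction-blind counting**

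If the scan carried no information about birth weight, the rate as worded would be 10% + 10% = 20%. The direction-matched rate would be 10% for any mix of FGR and LGA calls. With an informative scan the gap closes quickly:

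| Correlation | Birth weight in same tail | Birth weight in opposite tail (inflation) |
|---|---|---|
| 0 | 10% | 10% |
| 0.2 | 17.2% | 4.8% |
| 0.3 | 21.6% | 3.0% |
| 0.4 | 26.7% | 1.6% |
| 0.5 | 32.4% | 0.7% |
| 0.7 | 46.8% | 0.04% |

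In this model, same-tail agreement of 67% needs a correlation of about 0.89, and 80% needs about 0.96. The opposite-tail share is then effectively zero (about 1 in 100 million at 0.89).

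**Step 3: how many women**

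At the planned rates, women with any abnormal finding number about 0.25 × 103 = 25.75 (26) in the intervention group and 0.10 × 103 = 10.3 (10) in the control group. These counts include women with fluid findings only, so they are upper limits for growth calls. As a guide to precision, 5 of 26 has an exact 95% CI of 7% to 39%.

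**The case against.** The case for leaving the text alone has four parts.

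- **It may only be loose phrasing.** The plan asks for a rate. It does not call a diagnosis confirmed or correct, and a reader could supply an unstated 'respectively', since section 2.1 uses the same shorthand for two diagnoses. This stands in part: the text is an incomplete definition and not a stated scoring rule. But nothing in section 3.4 says which reading applies, so the analyst would have to choose.
- **Wrong-direction births will be rare.** This stands. A reader might infer from the 20% against 10% comparison that the rate is badly inflated. That needs a scan unrelated to birth weight, and the accuracy cited in section 1.2 points the other way.
- **The size of the merging effect is assumed.** This also stands. The 30% and 60% are not in the documents. A reader might take 6.7 to 8.0 as the ratio of FGR to LGA calls, which would give (6.7 × 30% + 8.0 × 60%) / 14.7 = 46%, or 16 points above FGR. Those figures are correctly identified cases, so they cannot serve as the denominator of a predictive value.
- **Little depends on it.** The item is secondary, the numbers are small, and nothing forbids a cross-table. All true, and the reason for the low rating. Nor does Table 3 show harm from a mis-scored LGA label, since its LGA line depends on a weight threshold and not on the 90th percentile.

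None of this answers the narrower point: the rate as written does not say how often an FGR call or an LGA call was right.

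**Conclusion.** The point holds in a limited form. Secondary question 1 yields one rate that merges two diagnoses which the plan itself defines separately, and the outcome is missing from section 3.4.2. Merging is the main loss. Under the assumed 30% and 60% the pooled 41% misses one value by 11 points and the other by 19, and if the two predictive values were equal the merging would cost little. Direction-blind counting is a minor flaw: under 1 point at a correlation of 0.5 and negligible at the accuracy in section 1.2, given bivariate normality.

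A reader might infer that the trial's main result is affected. It is not: the primary outcome is defined without outcomes after birth, and the sample size rests on that outcome alone. This is a low-severity improvement.

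**What to change.** In section 2.2, replace the single rate with two: birth weight <10% among women with an FGR call, and birth weight >90% among women with an LGA call, each with an exact 95% CI. Add a cross-table of ultrasound class by birth-weight class, so that any opposite-direction births are visible. List this outcome in section 3.4.2.

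The cost is a sentence or so in each section. No new data are needed, because the question as written already requires birth weight. The downside is precision: splitting at most about 26 intervention and 10 control women by diagnosis leaves small denominators and wide intervals, and the report should present the rates as descriptive.

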5.1 Data collection

Data will be collected on premade data sheets (see attachment) by either the principal investigators or Maternal-Fetal Medicine fellows.

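### As written, one sign such as tenderness at a cesarean incision counts as wound infection, so a pre-labor cesarean without infection can be scored as a composite maternal morbidity event

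*Combined protocol and SAP*

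**What the plan says.** Section 2.2 builds the maternal composite from single components, any one of which is sufficient: "CMM is defined as any of the following: 1) chorioamnionitis, 2) cesarean delivery in labor, 3) wound infection, 4) transfusion", followed by thromboembolism, intensive care admission and death. The same section then gives the rule for the third component: "Wound infection defined as tenderness, erythema, or discharge associated with cesarean skin incision". It cites two textbook chapters for the maternal definitions.

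Two other definitions in section 2.2 ask for more. For chorioamnionitis: "Chorioamnionitis defined as clinical findings of maternal fever, and maternal and fetal tachycardia in the absence of other localizing signs of infection". For the bowel component of the neonatal composite: "Necrotizing enterocolitis was diagnosed in the presence of more than one clinical sign", and a radiographic finding is needed as well.

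Section 3.4.2 lists "Composite Maternal Morbidity (CMM) among the two groups" as one of two secondary outcomes. Section 3.4.3 adds "Each secondary outcome will be analyzed similarly", which means a relative risk with a 95% confidence interval. It gives the purpose of the secondary outcomes as unbiased estimation to inform a larger multicenter trial. On ascertainment, section 5.1 states: "Data will be collected on premade data sheets (see attachment) by either the principal investigators or Maternal-Fetal Medicine fellows". That data sheet is not part of the text available for this review.

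**The concern.** The three signs are joined by *or*, and nothing else in the available text adds a second sign, a diagnosis, treatment, purulence or a time window. Tenderness is an ordinary finding at a new surgical wound, so the rule as worded can be met by a woman who is healing normally.

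Where this bites is narrow. The composite counts cesarean only when it occurs in labor. The wound rule can bring pre-labor cesareans back in on the strength of a chart entry. Such deliveries can be expected, since section 2.5.2 does not exclude women with a prior cesarean.

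The added events need not be balanced between arms. Section 3.1 has clinicians told the scan findings, Table 1 marks scheduled cesarean as an option for both growth abnormalities, Table 3 includes a cesarean recommendation for large fetuses above a stated weight, and section 2.4 expects abnormalities to be detected in 25% versus 10% of women. Serial scanning could therefore change the number of pre-labor cesareans and, through this rule, the CMM count, with no change in infection. The sign is subjective, and no masking of the abstractors to arm is described.

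At stake is how cleanly a secondary outcome is estimated when the plan wants that estimate for designing a later trial.

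**Working it through.** **1. The plan's own figures.** The documents give no rate for CMM, wound infection or cesarean, so there is no CMM figure to reproduce. The size figure in section 2.4 reproduces with the two-sided unpooled formula:

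n = (1.960 + 0.842)² × (0.10×0.90 + 0.25×0.75) / 0.15² = 7.849 × 0.2775 / 0.0225 = 96.8, so 97 per arm and 194 in total. With 5% loss, 97 / 0.95 = 102.1, so 103 per arm and 206 in total.

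CMM does not enter this calculation, so the sample size is unaffected.

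**2. The written rule applied to four records.**

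- Cesarean in labor, tender incision: already an event through component 2. The wound rule changes nothing.
- Pre-labor cesarean, tenderness charted, normal healing, no other listed component: an event, through wound infection.
- The same course with no note of tenderness: not an event.
- Vaginal birth: the rule cannot apply.

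The second and third records differ only in charting. Any miscount is therefore confined to pre-labor cesareans with no other CMM component.

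**3. Effect on the CMM rate and relative risk (illustration only).** For each arm let

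- b = true CMM rate,
- q = proportion of women with a pre-labor cesarean and no other CMM component,
- t = share of those women scored as wound infection without being infected.

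Observed rate = b + q×t. Observed RR = (b_serial + q_serial×t) / (b_control + q_control×t). Added events per arm of 103 = 103×q×t.

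All values of b, q and t below are assumptions.

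| Assumed case | t = 5% | t = 25% | t = 50% | t = 100% |
|---|---|---|---|---|
| Added events per arm, q = 10% | 0.5 | 2.6 | 5.2 | 10.3 |
| b = 20% in both arms, q = 10% in both: observed rate | 20.5% | 22.5% | 25.0% | 30.0% |
| Same case: observed RR (true 1.00) | 1.00 | 1.00 | 1.00 | 1.00 |
| b = 15% serial, 20% control, q = 10% in both: observed RR (true 0.75) | 0.76 | 0.78 | 0.80 | 0.83 |
| b = 20% in both, q = 10% serial, 5% control: observed RR (true 1.00) | 1.01 | 1.06 | 1.11 | 1.20 |
| b = 20% in both, q = 5% serial, 10% control: observed RR (true 1.00) | 0.99 | 0.94 | 0.90 | 0.83 |

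Example, fifth row at t = 50%: (0.20 + 0.10×0.5) / (0.20 + 0.05×0.5) = 0.250 / 0.225 = 1.11.

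The RR is preserved only when the added events stand in the same ratio between arms as the true rates. Equal q with a true RR of 1 is one such case.

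**4. Scale against sampling error.** With 20% CMM in both arms of 103, SE(log RR) = √(2×0.80 / (0.20×103)) = √0.0777 = 0.279. The 95% interval therefore runs a factor of exp(1.96×0.279) = 1.73 either way. The largest shift in the table is a factor of 1.20.

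**The case against.** The strongest reply is that the term being defined is an infection. The three signs can be read as those by which a clinician recognizes infection, and section 5.1 gives abstraction to obstetric specialists or fellows. They may well not tick the item for a sore but healthy scar. The data sheet is not visible, and if it simply asks whether a wound infection occurred, the problem largely goes away. This stands as a limit on size: t could be close to zero. It does not rescue the text, because the written rule would then not be the one applied.

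Second, randomization should balance repeat cesareans. That also stands. Balanced pre-labor cesareans inflate the rate and dilute a true effect, but they leave a null RR at 1. A 5-point difference between arms would require one third of the 15-point difference in expected detection (25% minus 10%) to become pre-labor cesareans, and Table 3's visible cesarean recommendation applies only from an estimated weight of 5,000. The documents show a route to imbalance; they do not show that it would be large.

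Third, CMM is an unpowered secondary outcome, and the sentence about unbiased estimates follows a calculation for the neonatal composite only. The first part is right. On the second, that sentence refers to the secondary outcomes in the plural, so CMM is reasonably included.

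Fourth, requiring a documented diagnosis still depends on charting. That is true; the change makes the criterion more specific but does not remove that dependence.

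**Conclusion.** The point holds as a modest correction to a secondary outcome. Section 2.2 as written allows a single nonspecific sign to count as wound infection, so a pre-labor cesarean without infection can be scored as a CMM event. That can raise the CMM rate, dilute its relative risk, or move it if pre-labor cesarean differs by arm.

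A reader might go further and infer that uninfected women will enter the composite, or that the relative risk is biased by a known amount. The documents support neither. Every figure in the table rests on assumed CMM, cesarean and scoring rates, and both the size and the direction are unknown. If only diagnosed infections are recorded, the effect is near nil. The illustrated shifts are also smaller than the sampling uncertainty at 103 per arm. The primary outcome, its analysis and the sample size are not affected.

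**What to change.** In section 2.2, for scoring CMM, define wound infection as a clinician's documented diagnosis of cesarean wound infection or purulent discharge from the incision, and state that tenderness or erythema alone does not count. Add a field to the data sheet for the criterion that was met, and report the component by arm beside the composite.

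The cost is one sentence, one data field and one reported line, with no extra women or procedures. The small downside is that a mild infection with neither a recorded diagnosis nor purulent discharge would be missed. Any relative-risk figures used to explain the change should be labelled as illustrations under assumed rates.
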